5.2.2. Prior and Concomitant Medications

The number and percentage of subjects who received prior and concomitant medications will be summarized by WHO drug anatomical therapeutic chemical (ATC) (March 2016) classification level 3 and PT. Medications are considered prior if they are received prior to the first dose of study drug (start date is prior to the first dose of study drug or in the case of antifungals if the start date and time is prior to the date and time of the first dose of study drug) or if the start date is unknown. Medications are considered concomitant if they are received on or after the first dose of study drug (start date/time is on or after the first dose of study drug, stop date/time is after the first dose of study drug), or if the stop date is unknown or continuing.

The number and percentage of subjects who receive the following categories of prior and concomitant medications will be summarized by treatment group in the mITT population for Parts A and B combined:

- Systemic antifungal medications received prior to the first dose of study drug and given for indication of either candidemia or IC.
- Systemic antifungal medications (excluding study drug) received on/after the first dose of study drug through the FU visit and given for indication of either candidemia or IC.

By subject listings for non-antifungal medications and antifungal medications received prior to the first dose or administered after the first dose of study drug through the FU visit will be provided separately for the Safety population.

5.2.3. Concomitant Procedures

Concomitant procedures will be summarized by treatment group, SOC, and PT using version 19.0 of MedDRA in the mITT population. If the same procedure (based on PT) is

CONFIDENTIAL Page 37 of 56

reported for the same subject more than once, the medical/surgical history is counted only once for that PT. Procedures are considered concomitant if they are performed on or after the first dose of study drug (start date/time is on or after the first dose of study drug, stop date/time is after the first dose of study drug), or if the stop date is unknown or continuing.

A by-subject listing will display procedures on/after the first dose of study drug through the FU visit and will include the verbatim description of the procedure, MedDRA PT, reason for the procedure, and date and time of the procedure.

5.3. Analysis of Efficacy

All efficacy analyses will be conducted in the mITT population for Part A, Part B, and Parts A and B combined, unless otherwise specified. Subjects will be analyzed in the treatment group to which they were randomized. By subject listings of the overall response, Investigator's assessment of response and systemic signs and symptoms assessments will be provided.

5.3.1. Primary Efficacy Outcome - Overall Success at Day 14 (±1 day)

The number and percentage of subjects programmatically determined to be an overall success (mycological eradication and resolution of clinical signs of candidemia and/or IC), failure, or with an indeterminate overall response at Day 14 (±1) will be summarized by treatment group for subjects in the mITT population. Exact 2-sided 95% CIs for the percentage of subjects who achieve success in each treatment group will be determined using the Clopper-Pearson method.

The overall response summary at Day 14 (± 1 day) will also be summarized separately for the following subgroup analyses defined in Section 3.8:

- Diagnosis of candidemia only and IC (with or without candidemia)
- Geographic Region
- Hepatic Insufficiency at Screening
- Renal Function Status at Screening
- Renal Disease at Screening
- Prior antifungal therapy activity
- APACHE II score
- Catheter status at Baseline

For these subgroup analyses, exact 2-sided 95% CIs for the percentage of subjects who achieve success in each treatment group within the subgroups will be determined using the Clopper-Pearson method. If the number of subjects in the subgroup overall is <10, 95% CI will not be provided for the percentage of subjects who achieve success. The subgroup analyses by prior antifungal therapy, APACHE II score, and catheter status will only be summarized for Parts A and B combined.

The reasons for failure or indeterminate overall response at Day 14 (± 1) will be summarized by treatment group for all subjects in the mITT population with an overall response of failure or indeterminate at Day 14 (± 1).

A summary will be provided for overall response at Day $14 (\pm 1)$ excluding those subjects in the mITT population who received more than 1 dose of a concomitant antifungal (with the exception of subjects who received a rescue antifungal for the treatment of candidemia) up

CONFIDENTIAL Page 38 of 56

through Day 14 (±1) in addition to study drug. This subset to be excluded is described in Section 3.8. Exact 2-sided 95% CIs for the percentage of subjects who achieve success in each treatment group will be determined using the Clopper-Pearson method.

A summary of overall response at Day 14 (±1) will be provided for Parts A and B combined in the mITT2 and mITT3 populations and for subjects in the mITT2 and mITT3 populations without prior antifungal therapy. Exact 2-sided 95% CIs for the percentage of subjects who achieve success in each treatment group will be determined using the Clopper-Pearson method. If the number of subjects in a category (with prior antifungal therapy or without prior antifungal therapy) is <10, 95% CI will not be provided for the percentage of subjects who achieve success in that category.

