3. GENERAL STATISTICAL METHODS

3.1. Sample Size Justification

This is an exploratory study and therefore, is not powered for inferential statistical analyses. A sufficient number of subjects are randomized to the CD101 IV and IV caspofungin treatment groups in Part A to provide an initial, substantive analysis of safety, tolerability, and estimate efficacy.

It is expected that approximately 114 subjects in Part A will need to be randomized given an estimated discontinuation rate of 20%, in order to achieve 90 evaluable subjects in the mITT population. In Part A, assuming a 73% overall success rate, the sample size of 30 subjects in the mITT population in each CD101 IV treatment group and the IV Caspofungin group will yield a 95% confidence interval (CI) for this success rate of 53.8% to 87.5%.

The addition of Part B in Amendment 5 of the protocol increased the study sample size by approximately 50% to 130% (depending on the rate of enrollment over the additional months to the staged start of the Phase 3 study and the rolling close-out of Part B). In Part B, subjects will be randomized until there are at least 30 subjects in the CD101 IV treatment groups at any dose and 30 subjects in the comparator group (≥45 additional subjects and no more than 120 subjects). In Part B, total enrollment will depend on the enrollment rate for the period between the end of Part A and the start of the Phase 3 study. With the addition of Part B subjects and assuming a 73% overall success rate, a total approximate sample size of 60 subjects in the CD101 treatment group (consisting of Group 1 from Amendment 5 and Group 2 from Amendment 6) will yield a 95% CI of 60.0% to 83.7%, and a total approximate sample size of 110 subjects in the CD101 treatment group (consisting of Group 1 from Amendment 5 and Group 2 from Amendment 6) will yield a 95% CI of 63.7% to 81.0%.

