5.3.3.2. Time to Negative Blood Culture

The time to negative blood culture (hours) will be analyzed using Kaplan-Meier methodology by treatment group, and for the CD101 treatment groups combined, in the mITT population. Summaries will include the 25th, 50th (median), and 75th percentiles. The number and percentage of subjects censored and the reason for censoring (receipt of more than 1 dose of non-study antifungal for the treatment of candidemia and/or IC [with the exception of a rescue antifungal],

CONFIDENTIAL Page 41 of 56

lost to follow up prior to having 2 negative blood cultures) will also be provided. A graph of the Kaplan-Meier curves will be provided.

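### SAP Section 3.1 states the Parts A+B precision for a CD101 group mixing two doses, but the primary table in Section 5.3.1 reports each randomized dose separately, so the precision should be restated per dose.

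*SAP*

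**What the plan says.** Section 3.1 offers precision, not power, as the reason for the sample size. For Part A it works per randomized group: "assuming a 73% overall success rate, the sample size of 30 subjects in the mITT population in each CD101 IV treatment group" and the caspofungin group, with a "confidence interval (CI) for this success rate of 53.8% to 87.5" percent.

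For the trial enlarged by Part B it changes the unit. The lower figure is for "60 subjects in the CD101 treatment group (consisting of Group 1 from Amendment 5 and Group 2 from Amendment 6"), which "will yield a 95% CI of 60.0% to 83.7" percent. The upper figure is for 110 subjects in a CD101 group described in the same way, with 63.7% to 81.0%.

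Sections 1.2.1 and 1.2.2 define groups 1 and 2 as different regimens and separate randomized groups. In Part B, subjects under Amendment 5 are randomized 2:1 to group 1 or caspofungin, and subjects under Amendment 6 are randomized 2:1 to group 2 or caspofungin.

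Section 5.3 runs the efficacy analyses "for Part A, Part B, and Parts A and B combined, unless otherwise specified" and keeps subjects in the group to which they were randomized. Section 5.3.1 tabulates the primary outcome by treatment group: "Exact 2-sided 95% CIs for the percentage of subjects who achieve success in each treatment group will be determined". Section 3.5 pools over sites and, for selected analyses, over the two parts. It does not mention pooling over doses.

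Where the SAP wants the doses together it says so. Time to negative blood culture (Section 5.3.3.2) is analysed "by treatment group, and for the CD101 treatment groups combined, in the mITT population". The tables of frequent adverse events (5.4.1) and some plasma concentration summaries (5.3.4) also name a combined CD101 group.

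**The concern.** Section 5.3.3.2 lists the treatment groups and the combined CD101 groups as two separate things. The phrase used in 5.3.1 therefore cannot be read as silently including the combination, and none of the primary or secondary response-rate analyses in 5.3.1 and 5.3.2 adds it.

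The precision given for the enlarged trial thus describes a mixed-dose group, while the table it is meant to justify has one column per dose. Precision is the only sample-size argument in the plan. A reader who takes 60.0% to 83.7% or 63.7% to 81.0% as the accuracy to expect for a CD101 regimen may expect too much, by an amount that depends on how Part B divides between Amendments 5 and 6. The SAP does not give that division.

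**Working it through.** **Inputs.** From Section 3.1: success rate 73%; 30 mITT subjects per group in Part A; Part B between 45 and 120 subjects; CD101 totals of 60 and 110. From Sections 1.2.1 and 1.2.2: 2:1 allocation in Part B, with group 1 under Amendment 5 and group 2 under Amendment 6. From Section 3.2: exact two-sided 95% Clopper-Pearson intervals.

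**Assumptions.** The Amendment 5/6 split is not stated, so a range is shown. All Part B subjects are counted in the mITT population; any exclusions would widen the intervals. Section 3.1 also asks for 30 comparator subjects in Part B, which does not fit 2:1 at a total of 45. The 2:1 ratio is used here, and that mismatch is a separate matter.

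**Formula.** With x = 0.73n, the lower limit is the 2.5% quantile of Beta(x, n − x + 1), and the upper limit is the 97.5% quantile of Beta(x + 1, n − x).

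**Step 1: reproduce the plan's figures.**

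| n | x = 0.73n | 95% CI | Width (points) |
|---|---|---|---|
| 30 | 21.9 | 53.8% to 87.5% | 33.7 |
| 60 | 43.8 | 60.0% to 83.7% | 23.7 |
| 110 | 80.3 | 63.7% to 81.0% | 17.3 |

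All three agree with Section 3.1, so the arithmetic is not in question.

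**Step 2: see where 60 and 110 come from.** Part B CD101 subjects number 2/3 × 45 = 30, or 2/3 × 120 = 80. Then 30 + 30 = 60 and 30 + 80 = 110. Each total is one Part A dose group plus all Part B CD101 subjects, which fits a Part B that uses a single dose.

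**Step 3: per-dose size and interval for Parts A+B.** Each dose has 30 subjects from Part A plus its share of Part B.

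| Part B total | Split of Part B CD101 subjects | n per dose | 95% CI (width) for each |
|---|---|---|---|
| 45 | 0 / 30 | 30 and 60 | 53.8% to 87.5% (33.7); 60.0% to 83.7% (23.7) |
| 45 | 8 / 22 | 38 and 52 | 56.2% to 86.1% (29.9); 58.9% to 84.4% (25.5) |
| 45 | 15 / 15 | 45 and 45 | 57.7% to 85.1% (27.4) |
| 120 | 0 / 80 | 30 and 110 | 53.8% to 87.5% (33.7); 63.7% to 81.0% (17.3) |
| 120 | 20 / 60 | 50 and 90 | 58.6% to 84.6% (26.0); 62.6% to 81.8% (19.2) |
| 120 | 40 / 40 | 70 and 70 | 61.1% to 82.9% (21.9) |

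At each Part B size the stated width appears only in the row where one dose takes all Part B CD101 subjects. In that row the other dose stays at its Part A size of 30.

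**Step 4: test the full pool.** Both doses over both parts hold 60 + 30 = 90 to 60 + 80 = 140 subjects, giving 62.6% to 81.8% (width 19.2) to 64.9% to 80.1% (15.3). These are not the 60 and 110 of Section 3.1 either.

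**The case against.** The strongest reply is that the stated intervals can match a reported column. Section 1.2.1 has Amendment 5 randomizing until group 1 reaches at least 30 subjects. If that happened, group 1 would have 30 + 30 = 60 over both parts, exactly the size behind 60.0% to 83.7%. A larger Part B could also bring one or both doses to 60 or more; at 120 with an equal split, each dose has 70 and a width of 21.9 points, narrower than 23.7. This stands. A reader might infer that the stated precision can belong to no planned result, or is always tighter than a dose column can achieve, and the SAP does not support that. But Section 3.1 counts its Part B minimum over CD101 groups at any dose and describes the 60 and 110 as a mixture, so the single-dose case is one possibility among several.

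A second reply is that the trial is exploratory and descriptive, with no power claim and no multiplicity concern (Sections 3.1 and 3.7). That is true, and no test or adjustment is asked for here. Precision is still the justification given, so it should describe what will be tabulated.

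A reader might also infer from the objective in Section 1.1.2, worded for CD101 IV as a whole, that a dose-pooled rate must be the primary summary. The SAP does not require this. The groups are different regimens, and the Part B regimen changed after the unblinded Part A analysis. Reporting by randomized group is sound, and pooling is a debatable choice. Nor does having several dose-by-part rates show bias in itself, since all of them are to be tabulated.

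**Conclusion.** The point holds as a mismatch between Section 3.1 and Section 5.3.1. The Parts A+B precision is stated for a mixed-dose CD101 group, whereas the primary table reports each dose. At Part B totals of 45 and 120, a dose column attains the stated 23.7 or 17.3 points only if all Part B CD101 subjects receive that dose. With an equal split the widths are 27.4 and 21.9 points, which is 3.7 and 4.6 points wider. At the extreme, one dose remains at 33.7 points. These sizes rest on a 73% success rate, 30 subjects per dose from Part A, 2:1 allocation, all Part B subjects in the mITT population, and splits that are assumptions. The arithmetic in Section 3.1 and the by-group analysis in Section 5.3.1 are both sound; what needs correcting is the description of the group to which the intervals apply.

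**What to change.** In Section 3.1, replace the two mixed-group statements with the Parts A+B precision per dose at 73% success, over the possible Amendment 5/6 splits and labelled as assumptions:

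- Part B of 45: n per dose from 30 (53.8% to 87.5%) to 60 (60.0% to 83.7%); equal split of 45 per dose, 57.7% to 85.1%.
- Part B of 120: n per dose from 30 (53.8% to 87.5%) to 110 (63.7% to 81.0%); equal split of 70 per dose, 61.1% to 82.9%.

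If the sponsor also wants a pooled CD101 summary, add it to Section 5.3.1 as a supportive column beside the dose columns, with its own size and interval: about 62.6% to 81.8% at n = 90 to 64.9% to 80.1% at n = 140. The intervals for 60 and 110 must not be attached to that column.

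The cost is a few sentences of SAP text and, if chosen, one extra column. Conduct and data collection do not change. The drawback is that the stated per-dose precision becomes less favourable in most splits.

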5.3.2. Secondary Efficacy Outcomes

5.3.2.1. Overall Response at Day 5, Day 28 (± 2) and Follow-up

The number and percentage of subjects with an overall success, failure, and indeterminate response at Day 5 and FU will be summarized by treatment group for subjects in the mITT population. The overall response summary will also be performed by diagnosis. The overall response at Day 5 and FU will be performed for subjects with candidemia only in the mITT population and at Day 5, Day 28 and FU for subjects with IC (with or without candidemia) in the mITT population. Exact 2-sided 95% CIs for the percentage of subjects who achieve success in each treatment group will be determined using the Clopper-Pearson method. If the number of subjects with IC overall is <10, 95% CI will not be provided for the percentage of subjects who achieve success.

An additional analysis of overall response at FU will be conducted excluding subjects who received more than 1 dose of a concomitant antifungal (with the exception of subjects who received a rescue antifungal for the treatment of candidemia and/or IC) up through Day 21 (for subjects with candidemia only) or Day 28 (for subjects with IC, with or without candidemia) or who receive more than 1 dose of a non-study antifungal after Day 21 or Day 28 for the treatment of an infection other than candidemia and/or IC. This subset to be excluded is described in Section 3.8. Exact 2-sided 95% CIs for the percentage of subjects who achieve success in each treatment group will be determined using the Clopper-Pearson method.

The overall response summary at Day 5 and Follow-up will also be summarized separately for the following subgroup analyses defined in Section 3.8:

- Diagnosis of candidemia only and IC (with or without candidemia)
- Geographic Region
- Hepatic Insufficiency at Screening
- Renal Function Status at Screening
- Renal Disease at Screening

Additionally, the overall response summary at Day 28 (± 2) will be summarized only for diagnosis of IC (with or without candidemia). For each subgroup analyses, exact 2-sided 95% CIs for the percentage of subjects who achieve success in each treatment group within the subgroups will be determined using the Clopper-Pearson method. If the number of subjects in the subgroup overall is <10, 95% CI will not be provided for the percentage of subjects who achieve success.

CONFIDENTIAL Page 39 of 56

5.3.2.2. Mycological Response at Day 5, Day 14 (± 1), Day 28 (± 2) and Follow-up

The number and percentage of subjects programmatically determined as having a mycological success (eradication), failure, or with an indeterminate mycological response at Day 5, Day 14 (±1), and FU will be summarized, by treatment group for subjects in the mITT population. Exact 2-sided 95% CIs for the percentage of subjects who achieve success in each treatment group will be determined using the Clopper-Pearson method. If the number of subjects with IC overall is <10, 95% CI will not be provided for the percentage of subjects who achieve success.

The mycological response summary at Day 5, Day 14 (± 1), and Follow-up will also be summarized separately for the following subgroup analyses defined in Section 3.8:

- Diagnosis of candidemia only and IC (with or without candidemia)
- Geographic Region
- Hepatic Insufficiency at Screening
- Renal Function Status at Screening
- Renal Disease at Screening
- Prior antifungal therapy activity
- APACHE II score
- Catheter status at Baseline

Additionally, the mycological response summary at Day 28 ± 2 will be summarized only for diagnosis of IC (with or without candidemia). For each subgroup analyses, exact 2-sided 95% CIs for the percentage of subjects who achieve success in each treatment group within the subgroups will be determined using the Clopper-Pearson method. If the number of subjects in the subgroup overall is <10, 95% CI will not be provided for the percentage of subjects who achieve success. The subgroup analyses by prior antifungal therapy, APACHE II score, and catheter status will only be summarized for Parts A and B combined.

5.3.2.3. Investigator's Assessment of Clinical Response at Day 14 (±1), Day 28 (±2), and the Follow-up Visit

The number and percentage of subjects determined by the PI to be a clinical cure, failure, or with an indeterminate clinical response at Day 14 (±1) and at the FU visit will be summarized by treatment group for subjects. The Investigator's assessment of clinical response will also be provided by diagnosis. The Investigator's assessment of clinical response at Day 14 and FU will be performed for subjects with candidemia only in the mITT population and at Day 14, Day 28, and FU for subjects with IC (with or without candidemia) in the mITT population. Exact 2-sided 95% CIs for the percentage of subjects who achieve cure in each treatment group will be determined using the Clopper-Pearson method. If the number of subjects with IC overall is <10, 95% CI will not be provided for the percentage of subjects who achieve success.

The reasons for failure or indeterminate clinical response at Day 14 (± 1) and FU visit will be summarized by treatment group for all subjects in the mITT population.

An additional analysis of clinical response at FU will be conducted excluding subjects who received more than 1 dose of a concomitant antifungal (with the exception of subjects who received a rescue antifungal for the treatment of candidemia and/or IC) up through Day 21 (for subjects with candidemia only) or Day 28 (for subjects with IC, with or without candidemia) or

CONFIDENTIAL Page 40 of 56

who receive more than 1 dose of a non-study antifungal after Day 21 or Day 28 for the treatment of an infection other than candidemia and/or IC. This subset to be excluded is described in Section 3.8. Exact 2-sided 95% CIs for the percentage of subjects who achieve success in each treatment group will be determined using the Clopper-Pearson method.

The clinical response summaries will also be stratified separately for the following subgroup analyses defined in Section 3.8:

- Diagnosis of candidemia only and IC (with or without candidemia)
- Geographic Region
- Hepatic Insufficiency at Screening
- Renal Function Status at Screening
- Renal Disease at Screening
- APACHE II score
- Catheter status at Baseline

For these subgroup analyses, exact 2-sided 95% CIs for the percentage of subjects who are determined to be a cure in each treatment group within the subgroups will be determined using the Clopper-Pearson method. If the number of subjects in the subgroup overall is <10, 95% CI will not be provided for the percentage of subjects who achieve success. The subgroup analyses by APACHE II score and catheter status will only be summarized for Parts A and B combined.

A summary of subjects determined by the PI to be a clinical cure, failure, or with an indeterminate clinical response at Day 14 (± 1) and at the FU visit will be provided for Parts A and B combined in the mITT2 and mITT3 populations and for subjects in the mITT2 and mITT3 populations without prior antifungal therapy. Exact 2-sided 95% CIs for the percentage of subjects who achieve success in each treatment group will be determined using the Clopper-Pearson method.

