Subjects randomized to the CD101 IV treatment group 1 will receive 1 dose of CD101 IV (400 mg) over 60 (±10) minutes on Day 1 and Day 8 and IV placebo on other study days in order to maintain the blind; subjects who require >14 days of IV therapy will receive an optional third dose of CD101 IV (400 mg) on Day 15. Subjects with IC are allowed an optional CD101 IV dose (400 mg) on Day 22 if additional therapy is required. Subjects in group 1 will receive IV placebo on other study days in order to maintain the blind. Subjects randomized to the CD101 IV treatment group 2 will receive 1 dose of CD101 IV (400 mg) over 60 (\pm 10) minutes on Day 1, 200 mg on Day 8 and IV placebo on other study days in order to maintain the blind; subjects who require >14 days of IV therapy will receive an optional third dose of CD101 IV (200 mg) on Day 15. Subjects with IC are allowed an optional CD101 IV dose (200 mg) on Day 22 if additional therapy is required. Subjects in group 2 will receive IV placebo on other study days in order to maintain the blind. Subjects may receive oral step-down therapy after ≥3 days of IV therapy, if criteria are met. Step-down therapy in both CD101 IV treatment groups will be oral placebo, in order to maintain the blind. Subjects who have already switched to oral step-down therapy will receive both oral placebo and CD101 IV on Day 8 and optional oral placebo and CD101 IV on Day 15 for subjects who require >14 days of therapy. Dosage adjustments are not allowed. Intravenous study drug is administered 24 (±2) hours after study drug was administered on the previous day.

Subjects randomized to the caspofungin group will receive IV caspofungin (70 mg loading dose on Day 1 and then 50 mg/day) for ≥ 3 days up to a maximum of 21 days for subjects with candidemia only or up to a maximum of 28 days for subjects with IC. After ≥ 3 days of IV therapy, subjects in the IV caspofungin group can be switched to oral step-down therapy if criteria are met. Step-down therapy in the caspofungin treatment group will be oral fluconazole (a loading dose of 800 mg [4 capsules] on the first day followed by 400 mg [2 capsules]/day thereafter). In order to maintain the blind, subjects who have already switched to oral step-down therapy will receive both oral fluconazole and IV placebo on Day 8, Day 15 for subjects who require ≥ 14 days of therapy. Intravenous study drug is administered 24 (± 2) hours after study drug was administered on the previous day.

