5.3.4. CD101 Plasma Concentration

Summary statistics (number of subjects, mean, SD, coefficient of variability % (CV%), median, min, max, geometric mean) of CD101 plasma concentration will be provided by time point and dose group for CD101 treated subjects in the PK population. Each CD101 dose group will be summarized separately for all timepoints and combined for all timepoints except Day 15. Only samples collected on Day1, Day 2, Day 4, Day 8 and Day 15 and within 10% of the nominal time (where applicable) will be included. Analyses of CD101 plasma concentration will only be conducted for Part A.

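### The two CD101 groups have the same planned treatment until the Day 8 dose, yet Day 5 overall and mycological response are estimated only by separate group, which gives up precision

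*SAP*

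**What the plan says.** **Treatment (SAP 1.2.1).** In group 1 each active dose is 400 mg, and the schedule is worded "minutes on Day 1 and Day 8 and IV placebo on other study days in order to maintain the blind". Group 2 opens with the same Day 1 dose: "Subjects randomized to the CD101 IV treatment group 2 will receive 1 dose of CD101 IV (400 mg) over 60". Its text then departs from that of group 1 only in the second dose, where it reads "minutes on Day 1, 200 mg on Day 8 and IV placebo on other study days". Subjects who switch to oral treatment do not differ either: "Step-down therapy in both CD101 IV treatment groups will be oral placebo". The first planned difference is 400 mg against 200 mg at the Day 8 dose.

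**Day 5 reporting.** In SAP 5.3.2.1, overall success, failure and "indeterminate response at Day 5 and FU will be summarized by treatment group". In SAP 5.3.2.2, mycological success, failure and "indeterminate mycological response at Day 5, Day 14 (±1), and FU will be summarized, by treatment group". Both sections attach exact 95% intervals to each treatment group.

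**Where the SAP does combine the groups.** Time to negative blood culture (5.3.3.2) is summarised by group and also "for the CD101 treatment groups combined". Plasma concentration (5.3.4) is given separately and "combined for all timepoints except Day 15". The tables of treatment-emergent adverse events occurring in at least 5% of subjects (5.4.1) use the combined CD101 groups.

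**Window.** In Table 3-2 the Day 5 efficacy window runs from Study Day 5 to Study Day 9.

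**The concern.** Up to the Day 8 dose, groups 1 and 2 are two random samples from the same population on the same treatment. A Day 5 response rate taken in that period has one true value for CD101, and the best estimate of it uses both groups. In Part A, each by-group estimate uses only half the relevant subjects.

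The wording cannot be read as already covering a pooled column, because the SAP says so explicitly wherever it wants one.

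Two things are at stake. The first is precision: the study plans no tests, and its efficacy output is response rates with intervals, so an avoidably wide interval is a direct loss. The second is interpretation. Two small groups with the same planned treatment will often show visibly different rates by chance, and columns labelled by dose regimen leave those gaps open to being read as a dose effect. Part A is analysed in full, unblinded, before the study ends (SAP 3.13), so these columns would be seen while the study is still running.

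**Working it through.** **Inputs**
- Part A mITT size per CD101 group: 30 (SAP 3.1), so 60 for the two together.
- Success rate: 73% (SAP 3.1). The SAP states this for overall success and gives no Day 5 value. Using it at Day 5 is an assumption; 60% to 80% is used as a range.
- Interval: two-sided 95% Clopper-Pearson (SAP 3.2 and 5.3.2.1).

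**Step 1: reproduce the SAP's own figures.** With x = 0.73n successes (not rounded), the lower limit is the 2.5% quantile of Beta(x, n − x + 1) and the upper limit is the 97.5% quantile of Beta(x + 1, n − x).
- n = 30, x = 21.9: 53.8% to 87.5%, as stated in SAP 3.1.
- n = 60, x = 43.8: 60.0% to 83.7%, as stated.
- n = 110, x = 80.3: 63.7% to 81.0%, as stated.

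Whole counts change little: 22/30 gives 54.1% to 87.7%, and 44/60 gives 60.3% to 83.9%.

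**Step 2: gain from pooling at Day 5 in Part A.**
- By group, n = 30: 87.5 − 53.8 = 33.7 points.
- Combined, n = 60: 83.7 − 60.0 = 23.7 points.
- Reduction: 1 − 23.7/33.7 = 0.30, about 30% narrower.

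**Step 3: chance gaps between two groups of 30 with the same true rate.** The standard error of the difference at 73% is √(0.73 × 0.27 × (1/30 + 1/30)) = 0.115, or 11.5 points. A gap of at least 10 points means counts that differ by 3 or more; at least 20 points means 6 or more. Summing the exact joint binomial probabilities gives:

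| True rate | P(gap ≥ 10 points) | P(gap ≥ 20 points) |
|---|---|---|
| 60% | 51% | 15% |
| 73% | 47% | 11% |
| 80% | 42% | 7.5% |

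**Step 4: Parts A and B combined.** The split between the two CD101 groups is not fixed: Part B allocates to group 1 under Amendment 5 and to group 2 under Amendment 6. As an illustration only, with 60 in one group and 30 in the other at 73%, the chance of a gap of at least 10 points is 36%. The interval widths would be 23.7 points (n = 60), 33.7 points (n = 30) and 19.2 points (combined n = 90). The gain is then smaller for the larger group and greater for the smaller one.

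**Step 5: does every Day 5 assessment precede the differing dose?** Not necessarily. The Day 5 efficacy window ends at Study Day 9. The Day 8 visit itself has a window of ±1 day for subjects already stepped down and discharged (Table 1-1, footnote b). A windowed Day 5 assessment could therefore follow the 400 mg or 200 mg dose. The SAP gives no basis for estimating how many would.

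**The case against.** The strongest counter-argument is that a pooled measure of early clearance already exists. Time to negative blood culture is planned for the combined CD101 groups, for Part A, Part B and both together, and it needs two negative cultures at least 12 hours apart, close to the blood criterion for mycological success. This stands in part. That endpoint does not include resolution of systemic signs, so it cannot replace Day 5 overall response, and it leaves out subjects with invasive candidiasis whose only positive culture came from a sterile site.

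Three further objections stand as limits on the point:
- **A reader might infer that the SAP presents chance differences as dose effects.** It does not. The study is described as exploratory and descriptive, and 5.3.2.1 and 5.3.2.2 plan no difference, contrast or test between the CD101 groups. The risk is misreading.
- **A reader might infer that no dose difference can appear at Day 5, or that the sample is halved throughout.** The window to Study Day 9 rules out the first as an absolute statement. The second is exact only for Part A.
- **Pooling elsewhere does not prove a principle.** Adverse events are combined through follow-up, after the doses differ. Only the plasma concentration summary tracks identical dosing closely: the Day 8 sample is drawn before the dose (Table 1-1, footnote kk) and Day 15 is left out.

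Finally, a reader could add the by-group counts and compute the pooled interval. That shows how cheap the change is. It does not make the combined estimate part of the plan.

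**Conclusion.** The point holds as a modest one. Planned CD101 treatment is identical before the Day 8 dose, and the SAP names no combined CD101 estimate for the two Day 5 response endpoints. In Part A this leaves an interval of 33.7 points where 23.7 is available. By-group gaps of 10 points or more would arise by chance in close to half of such studies (47%; 42% to 51% over true rates of 80% to 60%).

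These figures assume that the 73% rate applies at Day 5 and that each Part A group reaches 30 mITT subjects. In Parts A and B combined the gain depends on group sizes that are not fixed. The claim of a common true rate is limited to assessments made before the Day 8 dose. Nothing in the two sections is misstated; the plan leaves available precision unused on secondary endpoints.

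**What to change.** In SAP 5.3.2.1 and 5.3.2.2:
1. Add a combined CD101 estimate with its Clopper-Pearson 95% interval for Day 5, for Part A and for Parts A and B combined. Place it beside the by-group columns, on the same mITT denominator and the same Day 5 window so that the columns add up.
2. Add a footnote that planned treatment in the two CD101 groups was identical before the Day 8 dose.
3. Report, by group, how many Day 5 assessments were made after the Day 8 dose, and repeat the combined estimate excluding those subjects.

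The cost is one extra column, one footnote and one small sensitivity row. No new data are needed, and the by-group results remain as planned.
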